3.1.3.1 Enrollment time

The investigators obtained the informed consent of the participants and signed the ICF, which was then screened according to the inclusion criteria. If the patient meets all the inclusion criteria of this trial and does not meet any of the exclusion criteria,

the case is included in this trial, and the time of enrollment of the subject is used as the treatment on the day of the first treatment, and a unique enrollment number is obtained in the order of enrollment.

3.1.3.2 The number of subjects required for the clinical trial

After screening according to the inclusion criteria, it is expected that a total of 47 subjects will be included in this clinical trial, all of whom will be treated with investigational medical devices.

3.1.4 Effectiveness evaluation methods

If it is not possible to follow up at the clinical trial center according to the visit arrangement due to the epidemic, the clinical examination can be examined by other tertiary hospitals, and the test results will be transmitted back to the clinical trial center for evaluation; The carrier of imaging data in the outer hospital is not limited, and it is necessary to ensure that the imaging department of the center can be opened and read.

3.1.4.1 The main effectiveness evaluation indicators and the methods and time selection of their evaluation, recording and analysis

(1) Tumor disease control rate (DCR).

Reason for selection: According to the clinical trial effectiveness evaluation in the "Guidelines for the Review of Clinical Evaluation Technologies of Proton Carbon Ion Therapy System" (CFDA Circular No. 4 [2018]): "In view of the local characteristics of radiotherapy, it is recommended that the efficacy evaluation should be based on local control, and according to the different diseases, the common standards in clinical research, such as the efficacy evaluation criteria for solid tumors, should be reasonably adopted RECIST. The efficacy evaluation can be divided into complete response CR, partial response PR, disease stable SD, disease progression PD, and the effective definition is: "CR+PR+SD." "; Due to the particularity of the disease, the evaluation method recommended in the relevant diagnosis and treatment guidelines is selected. The tumor disease

control rate was selected as the main effectiveness evaluation index, which was relatively objective and reproducible, and adopted the common standard in clinical research, which was widely recognized and applied by clinicians.

Definition of indicators: the occurrence of CR, PR and SD after the end of treatment is disease control; No biochemical recurrence at the end of prostate cancer treatment, no regional lymph nodes or distant metastases, considered disease control. Proportion of participants who developed disease control three months after the end of the last radiotherapy.

Metric type: Qualitative.

Data collection time: screening period, 3 months \pm 7 days after the end of the last treatment.

Evaluation time: 3 months \pm 7 days after the end of the last treatment.

Site of evaluation: Tumor receiving radiation therapy.

Evaluation method: The changes in tumor CT or MRI imaging before and after treatment were evaluated by an independent imaging review panel according to RECIST 1.1. At 3 months of radiographic evaluation, if PD is found, PET-CT is required to confirm it.

Calculation formula: DCR = number of disease control subjects / total number of subjects × 100%.

Criteria: See RECIST 1.1 for details. At the time of 3-month imaging evaluation, if the patient is found to have PD, PET-CT examination is required to confirm it, if progress is confirmed, it is recorded as PD, if progress cannot be confirmed, it may be false progression, and it is recorded as SD. If prostate cancer does not have biochemical recurrence, PET-CT examination is not required, and there is no metastasis by default, which is regarded as tumor control, and if biochemical recurrence occurs, it is regarded as tumor not controlled, and PET-CT is required to confirm tumor metastasis.

Note: Participants who aborted the trial for any reason (except loss to follow-up) before the end of the last radiation therapy were considered to have disease progression (PD) or were not controlled. Disease site evaluation uses the same approach as baseline, including consistent contrasted/non-contrast scans and prompt scanning. If changes are needed, the case must be discussed with a radiologist to determine whether an alternative approach is possible. If not, the objective situation in the future is unclear.

3.1.4.2 Secondary effectiveness evaluation indicators and their methods and timing of evaluation, recording, analysis

(1) Objective response rate (ORR).

Reason for selection: The Guidelines for the Review of Clinical Evaluation Technologies of Proton Carbon Ion Therapy Systems (CFDA Circular No. 4 [2018]) recommends the use of the latest version of the commonly used evaluation criteria for radiation oncology as the clinical trial evaluation criteria, so RECIST 1.1 is used Relevant indicators as effectiveness evaluation criteria; Due to the particularity of the disease, the evaluation method recommended in the relevant diagnosis and treatment guidelines is selected. All of them can directly measure the effect of radiotherapy and are widely recognized and applied by clinicians.

Definition of indicators: CR or PR after the end of treatment is considered objective remission, prostate cancer has no biochemical recurrence at the end of the last treatment, and no regional lymph nodes or distant metastasis are considered objective remission. Proportion of participants who experienced objective remission at each time point after the end of the last treatment.

Metric type: Qualitative.

Data collection time: screening period, 1 month \pm 7 days, 3 months, \pm 7 days after the end of the last treatment.

Evaluation time: 1 month \pm 7 days, 3 months, \pm 7 days after the last treatment.

Site of evaluation: Tumor receiving radiation therapy.

Evaluation method: The changes in tumor CT or MRI imaging before and after treatment were evaluated by an independent imaging review panel according to RECIST 1.1. At 3 months of radiographic evaluation, if PD is found, PET-CT is required to confirm it.

Calculation formula: ORR = number of subjects in objective response / total number of subjects × 100%.

Criteria: See RECIST 1.1 for details. At the time of 3-month imaging evaluation, if the patient is found to have PD, PET-CT examination is required to confirm it, if progress is confirmed, it is recorded as PD, if progress cannot be confirmed, it may be false progression, and it is recorded as SD. If prostate cancer does not have biochemical recurrence, PET-CT examination is not required, and there is no metastasis by default, which is regarded as objective remission, and if biochemical recurrence occurs, it is regarded as not objectively remission, and PET-CT is required to confirm tumor metastasis.

Note: Participants who aborted the trial for any reason (other than loss to follow-up) before the end of the last radiotherapy were considered to have not responded objectively. Disease site evaluation uses the same approach as baseline, including consistent contrasted/non-contrast scans and prompt scanning. If changes are needed, the case must be discussed with a radiologist to determine whether an alternative approach is possible. If not, the objective situation in the future is unclear.

(2) Time to sustained remission (DOR).

Reason for selection: The Guidelines for the Review of Clinical Evaluation Technologies of Proton Carbon Ion Therapy Systems (CFDA Circular No. 4 [2018]) recommends the use of the latest version of the commonly used evaluation criteria for radiation oncology as the clinical trial evaluation criteria, so RECIST 1.1 is used Relevant indicators as effectiveness evaluation criteria; Due to the particularity of the disease, the evaluation method recommended in the relevant diagnosis and treatment

guidelines is selected. They are all commonly used indicators for the evaluation of tumor treatment effects, and are widely recognized and applied by clinicians.

Indicator definition: the time between the first assessment of the tumour as CR or PR and the time between the first assessment of PD or death from any cause.

Indicator type: quantitative.

Data collection time: 1 month \pm 7 days, 3 months, \pm 7 days after the end of the screening period, until tumor progression or subject death.

Evaluation time: 3 months \pm 7 days after the last treatment.

Site of evaluation: Tumor receiving radiation therapy.

Evaluation method: The changes in tumor CT or MRI imaging before and after treatment were evaluated by an independent imaging review panel according to RECIST 1.1. At 3 months of radiographic evaluation, if PD is found, PET-CT is required to confirm it.

Calculation formula: DOR = time to death from PD or any cause on the first assessment - time to CR or PR for the first assessment;

Criteria: See RECIST 1.1 for details. At the time of 3-month imaging evaluation, if the patient is found to have PD, PET-CT examination is required to confirm it, if progress is confirmed, it is recorded as PD, if progress cannot be confirmed, it may be false progression, and it is recorded as SD.

Note: If no tumor progression or death is observed during the follow-up period after the end of radiotherapy, the formula is: DOR > last visit time after the end of the last radiotherapy - CR or PR time for first assessment. Others are the same as ORR.

(3) Tumor disease control rate (DCR).

Reason for selection: DCR 3 months after the end of the last treatment was the primary evaluation index, and DCR at other follow-up time was used as a secondary evaluation index.

Definition of indicators: the occurrence of CR, PR and SD after the end of treatment is disease control; No biochemical recurrence at the end of prostate cancer treatment, no regional lymph nodes or distant metastases, considered disease control. Proportion of participants who developed disease control at one month after the end of the last treatment.

Metric type: Qualitative.

Data collection time: screening period, 1 month \pm 7 days after the end of the last treatment.

Evaluation time: 1 month \pm 7 days after the last treatment.

Site of evaluation: Tumor receiving radiation therapy.

Evaluation method: The changes in tumor CT or MRI imaging before and after treatment were evaluated by an independent imaging review panel according to RECIST 1.1. At 3 months of radiographic evaluation, if PD is found, PET-CT is required to confirm it.

Calculation formula: DCR = number of disease control subjects / total number of subjects \times 100%.

Criteria: See RECIST 1.1 for details. At the time of 3-month imaging evaluation, if the patient is found to have PD, PET-CT examination is required to confirm it, if progress is confirmed, it is recorded as PD, if progress cannot be confirmed, it may be false progression, and it is recorded as SD. If prostate cancer does not have biochemical recurrence, PET-CT examination is not required, and there is no metastasis by default, which is regarded as tumor control, and if biochemical recurrence occurs, it is regarded as tumor not controlled, and PET-CT is required to confirm tumor metastasis.

Note: Participants who aborted the trial for any reason (other than loss to follow-up) before the end of the last radiotherapy were considered to have PD or was uncontrolled. Disease site evaluation uses the same approach as baseline, including consistent contrasted/non-contrast scans and prompt scanning. If changes are needed, the case must be discussed with a radiologist to determine whether an alternative approach is possible. If not, the objective situation in the future is unclear.

(4) Tumor markers (if needed)

Reason for selection: The Guidelines for the Review of Clinical Evaluation Technologies of Proton Carbon Ion Therapy System (CFDA Circular No. 4, 2018) suggests that changes in tumor markers and functional imaging parameters should be used as reference factors for effectiveness evaluation.

Data collection and evaluation time: screening period, 1 month \pm 7 days, 2 months \pm 7 days, 3 months \pm 7 months after the end of the last treatment Sky.

Evaluation method: tumor marker examination is performed, and the investigator judges that the tumor marker (before and after radiotherapy) is reported as clinically significant changes.

Note: Researchers choose relevant indicators according to the disease, and the scheme is not uniformly stipulated.

(5) Tumor-specific symptoms

Reason for selection: The Guidelines for the Review of Clinical Evaluation Technologies of Proton Carbon Ion Therapy Systems (CFDA Circular No. 4 of 2018) suggests that clinical manifestations should be recorded during follow-up.

Data collection and evaluation time: screening period, 1 month \pm 7 days, 2 months \pm 7 days, 3 months \pm 7 months after the end of the last treatment Sky.

Methodology: Symptoms are recorded according to the type of disease, which may include, but are not limited to, the following: pain, swallowing function, mobility, bleeding, visual acuity, appetite/weight, superficial lymph node size, and the investigator judges that the symptoms (before and after radiotherapy) are clinically significant.

Note: Researchers record relevant symptoms according to the disease, and the plan is not uniformly stipulated.

(6) Product usability evaluation (ProBeam system, radiotherapy management software (OIS), radiotherapy planning software (Eclipse)).

Reason for selection: Routine effectiveness indicators of medical device clinical trials.

Indicator type: quantitative, open-ended question.

Data collection and evaluation time: the day the last treatment was completed.

Evaluation method: Researchers using the corresponding function scored according to the Likrt scale and collected openended questions to evaluate the overall feeling of ease of use during treatment.

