	(4) Tumor recurrence rate (3 months ± 7 days after the end of the last treatment).
	(5) Incidence of adverse events (AEs) (3 months \pm 7 days after the end of the last
	treatment).
	(6) The incidence of Serious Adverse Events (SAEs) (3 months \pm 7 days after the end
	of the last treatment).
	(7) Incidence of device defects (after last treatment)
	Inclusion Criteria (Major Criteria):
	(1) $18 \leq age \leq 80$ years;
	(2) First-diagnosed patients with tumors of the nervous system, head and neck,
	chest, abdomen, spine, pelvic cavity, limbs, etc. by tissue/cell pathology;
	(3) ECOG physical condition is graded as 0 to 2;
	(4) Women of childbearing had negative results in the blood pregnancy test
	(Human Chorionic Gonadotropin, HCG) 7 days prior to the first treatment;
	(5) The subject or subject's guardian is able to understand the purpose of the
	study, demonstrate sufficient compliance with the protocol and sign informed
F1:_:L:1:4	consent form.
Eligibility	
criteria	Exclusion Criteria (Major Criteria):
	(1) The subject with radiotherapy contraindications, including the known genetic
	tendencies that increase the sensitivity of normal tissue radiotherapy or the
	accompanying diseases that lead to hypersensitivity to radiotherapy;
	(2) The subject with other uncontrolled tumors except that to be treated according
	to medical history or the investigator's estimation, or with other malignant tumors
	within five years prior to enrollment;
	(3) Implanted pacemakers or other metal prosthesis within the scope of proton
	therapy;
	(4) Other situations that investigator determines not suitable for enrollment.
Specifications	
for the use of	All subjects used the investigational medical devices Drade - from first and interest
investigational	All subjects used the investigational medical device: ProBeam for radiation therapy.
medical device	

Statistical analysis with SAS 9.4 software.

All data are described statistically, including baseline data, all efficacy measures, and all safety data. The measurement data give the mean, standard deviation, minimum, maximum, median, 25th quantile and 75th quantile; The counting data gives the frequency and composition ratio.

Effectiveness analysis

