3.1.2 Choice of trial method and justification

This trial was designed using the prospective, two-center, single-group target value method.

- (1) Prospective study: Adopt a research approach that traces from the present to the future. Prospective studies can establish cause and effect; There are unified diagnosis, detection and evaluation standards for the obtained data, so the data processing is controllable.
- (2) Two centers: Select 2 clinical trial institutions to carry out the clinical trial. More cases than single-center trials can be obtained in the same amount of time, thus shortening the duration of clinical trials.
- (3) Single-group target value method: Because the same device of the experimental medical device is radioactive and difficult to obtain, the existing treatment method is not feasible due to objective conditions, so the single-group target value method is adopted. Moreover, the applicable population and main evaluation indicators of experimental medical devices can be fully defined and relatively stable; The main evaluation index adopts the effective rate mentioned in the "Guidelines for the Technical Review of Clinical Evaluation of Proton Carbon Ion Therapy System" (CFDA Circular No. 4 [2018]), which is relatively objective and reproducible. According to the Guidelines for the Technical Review of Clinical Evaluation of Proton Carbon Ion Therapeutic response rate for experimental medical devices should be at least 80%, and the expected value should be 95%. Among them, the effective definition is: CR+PR+SD (complete response CR, partial response PR, disease stable SD), which is basically consistent with the definition of tumor disease control rate in this clinical trial. Therefore, no control group was set up in this clinical trial, and the single-group target value method was used to evaluate whether the tumor disease control rate reached the target value (80%) and the main safety evaluation index CTCAE 3 when ProBeam was used in

radiotherapy for tumor patients Whether the proportion of grade toxicities is less than acceptable (5%) and whether the proportion of CTCAE grade 4 and 5 toxicities is acceptable (0%).

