4.2 Sample size calculation

4.2.1 Total sample size

This clinical trial intends to enroll 47 subjects. The sample size determination process is as follows:

This clinical study is designed for clinical verification of a single group of target values, and the tumor disease control rate, the main effectiveness evaluation index, is used as the basis for sample size estimation. According to the Guidelines for the Review of Clinical Evaluation Technologies of Proton Carbon Ion Therapy System (CFDA Circular No. 4 of 2018), the target value is set at 80%, and the bilateral significance level is 0.05, and the power degree 80%, applying the sample size estimation professional software PASS 15.0, calculated by the above parameters, the test group needs a sample size of at least 42 cases. Considering that about 10% of cases may be dropped or lost to follow-up during clinical validation, the sample size of the experimental group was expanded to 47 cases.

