5.3.5 History of present tumor presentness

The history of present tumor will be summarized based on FAS. The indicators of present history of tumor include diagnosis basis, tumor type, tumor location, tumor status, pathological classification, and TNM stage. The frequency and composition ratio of the above categorical variables were calculated.

The list details the subject's present medical history.

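### The primary disease control rule for prostate cancer is stated in conflicting ways, and they disagree for a subject whose nodal or distant disease at entry persists at month 3 without biochemical recurrence

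*Protocol*

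**What the plan says.** **Definition.** The protocol summary, 3.1.4.1 and 3.1.4.2 (3) (disease control at 1 month) give the prostate rule as "No biochemical recurrence at the end of prostate cancer treatment, no regional lymph nodes or distant metastases, considered disease control". It has two conditions, and neither refers to status at entry.

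**Criteria.** Further on, 3.1.4.1 says: "If prostate cancer does not have biochemical recurrence, PET-CT examination is not required, and there is no metastasis by default", and regards such a subject as controlled. 3.1.4.2 (3) repeats this.

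**SAP.** Section 2.1.1 (primary DCR) and the 1-month DCR in 2.1.2 require only that there be no biochemical recurrence. For ORR, SAP 2.1.2 keeps the condition on nodal and distant metastasis. Section 6, which lists changes to the protocol analysis, covers only missing AE severity and missing AE relationship.

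**Eligibility.** The protocol summary, under a heading that marks the list as the major criteria, admits "First-diagnosed patients with tumors of the nervous system, head and neck" and other listed sites. It gives no limit on stage. The nearest exclusion concerns uncontrolled tumours other than the one to be treated. SAP 5.3.5 tabulates "tumor status, pathological classification, and TNM stage" at baseline.

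**Pass rule.** The lower limit of the Clopper-Pearson 95% interval for DCR must exceed 80% (protocol 4.5 and 4.7.1, SAP 5.4.1).

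**The concern.** Take a prostate subject with a positive node at screening that is still present and unchanged at month 3, and with no biochemical recurrence. Under the definition this subject is not controlled, because a regional node is present. Under the criteria the subject is controlled, because metastasis is presumed absent even though the baseline record shows it. Under the SAP the subject is controlled, because nodes are not considered.

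None of these rules measures change from baseline. For every other tumour, RECIST 1.1 compares imaging before and after treatment, and unchanged disease is SD and so counts as control. The prostate rule has no equivalent of SD. 3.1.4.1 also names the irradiated tumour as the site of evaluation, so a failure caused by a node outside the treated volume would not fit the endpoint's own scope.

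At stake is discretion over the primary endpoint: if such a subject is enrolled, the result depends on which sentence is applied, and the pass rule turns on single subjects.

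**Working it through.** **1. The plan's own sample size.** Protocol 4.2.1: "the target value is set at 80%, and the bilateral significance level is 0.05, and the power degree 80" per cent. Protocol 3.1.2: "the expected value should be 95" per cent. With the normal approximation for one proportion:

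n = [(z₀.₉₇₅·√(p₀(1−p₀)) + z₀.₈₀·√(p₁(1−p₁))) / (p₁−p₀)]²

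= [(1.960·√(0.80·0.20) + 0.842·√(0.95·0.05)) / 0.15]² = 41.6, so 42.

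This agrees with "the test group needs a sample size of at least 42 cases". Then 42/0.90 = 46.7, so 47, which agrees with "the sample size of the experimental group was expanded to 47 cases". The sample size is not at fault.

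**2. Failures allowed.** The Clopper-Pearson lower limit for x of n is the 0.025 quantile of Beta(x, n−x+1).

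| Controlled | Lower limit | Above 80%? |
|---|---|---|
| 44/47 | 82.5% | yes |
| 43/47 | 79.6% | no |
| 39/42 | 80.5% | yes |
| 38/42 | 77.4% | no |

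At either size, 3 failures pass and 4 do not.

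**3. The rules side by side,** for a prostate subject with nodal or distant disease at entry that persists at month 3, without biochemical recurrence.

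| Text | Conditions | DCR result |
|---|---|---|
| Protocol summary, 3.1.4.1 and 3.1.4.2 (3), definition | no biochemical recurrence; no nodal or distant metastasis | not controlled |
| Protocol 3.1.4.1 and 3.1.4.2 (3), criteria | no biochemical recurrence; metastasis presumed absent | controlled |
| SAP 2.1.1 and 2.1.2 | no biochemical recurrence | controlled |

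**4. Effect on the chance of passing.** The documents do not give the number of such subjects, k; I take k = 0 to 4 as an assumption. I also assume that each of the other N−k subjects is controlled with probability 0.95. Let r be the pass mark (44 at N = 47, 39 at N = 42).

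- Strict rule (definition): all k fail, so the chance is P[Bin(N−k, 0.95) ≥ r].
- Lenient rule (criteria, SAP): all k count as controlled, so the chance is P[Bin(N−k, 0.95) ≥ r−k].

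For N = 47 and k = 1, the strict rule allows at most 2 failures among 46:

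0.95⁴⁶ + 46·0.05·0.95⁴⁵ + 1035·0.05²·0.95⁴⁴ = 0.094 + 0.229 + 0.271 = 0.594.

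The lenient rule allows 3 failures among 46, which adds 15180·0.05³·0.95⁴³ = 0.209 and gives 0.803.

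| k | N = 47 strict | N = 47 lenient | N = 42 strict | N = 42 lenient |
|---|---|---|---|---|
| 0 | 0.793 | 0.793 | 0.843 | 0.843 |
| 1 | 0.594 | 0.803 | 0.663 | 0.853 |
| 2 | 0.335 | 0.813 | 0.399 | 0.862 |
| 3 | 0.105 | 0.824 | 0.135 | 0.871 |
| 4 | 0 | 0.833 | 0 | 0.880 |

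**The case against.** **The SAP settles it.** The SAP is dated after protocol 1.4 and says that it governs the short-term analysis. It agrees with the protocol's criteria, so two of the three rules score this subject as controlled. That carries weight, and it makes control the likelier scoring in practice. But the SAP does not say that it dropped a condition from the protocol's definition, and it keeps that condition for ORR. Its wording alone would also count as controlled a subject with new nodes at month 3 and no biochemical recurrence.

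**The criteria merely put the definition into operation.** This works for subjects without nodal or distant disease at entry. It does not work where the baseline record contradicts the presumption. The conflict is therefore confined to a corner case.

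**Such subjects may not exist.** A reader might infer that node-positive or metastatic prostate cancer is eligible. No text says so. Only the major criteria are shown, and the SAP cites a protocol section 8.7.2 for text that is numbered 4.7.2 here, so the public protocol may be abridged. Tabulating TNM stage covers all sites and proves nothing about prostate. What can be said is that the criteria shown do not exclude such subjects.

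**The magnitude is generic.** Any scoring dispute can flip a result at 43 versus 44 of 47. This is true. The PPS also prevails if it and the FAS disagree (SAP 5.6) and requires measurable lesions at baseline, so an affected subject may not be in it. This limits the weight of the point but does not remove the contradiction.

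**Conclusion.** The point holds as a conflict in the definition of the primary endpoint. The protocol's definition, the protocol's criteria and the SAP do not give one DCR rule for prostate cancer. They give opposite results for a subject with persisting nodal or distant disease and no biochemical recurrence.

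A reader might go further and infer that the result of such a subject is fixed at entry. The documents do not support that. Under the definition, status is read after treatment, so irradiated nodes could clear. Under the criteria and the SAP, biochemical recurrence decides. Only disease that persists, read literally under the definition, gives a certain failure.

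The size is conditional. With one such subject, the chance of passing at N = 47 is 0.80 under the lenient rules and 0.59 under the strict one; with four, passing is impossible under the strict one. This rests on an assumed number of affected subjects, which may be zero, and on 95% control in the others.

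**What to change.** Before database lock:

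1. **One DCR rule.** In the protocol summary, protocol 3.1.4.1 and 3.1.4.2 (3), and SAP 2.1.1 and 2.1.2, define prostate disease control as no biochemical recurrence, and no new or progressing nodal or distant disease compared with baseline TNM stage and imaging. The word progressing is needed, because a condition on new disease alone would ignore growth of an existing node.
2. **Limit the presumption.** Apply the presumption of no metastasis only to subjects without nodal or distant disease at entry. Score the others on the month-3 CT or MRI.
3. **Record it.** List the change in SAP section 6.
4. **Keep ORR separate.** Do not carry the no-new-disease wording over to ORR, where unchanged nodal disease would then count as remission although in other tumours it is only SD. For ORR, only reconcile the definition (protocol 3.1.4.2 (1), SAP 2.1.2) with the presumption in protocol 3.1.4.2 (1), so that unchanged nodal disease is not counted as remission.

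The cost is mainly wording in two documents. Baseline TNM stage is already tabulated, and 3.1.4.1 already bases the evaluation on imaging at screening and month 3. The trial flowchart is not shown, so confirm that it schedules the month-3 scan for prostate subjects.
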